4.3 Intervention

The primary aim is to assess the efficacy of ixazomib for the prevention of recurrent or late grade II-IV aGVHD or chronic GVHD at 1-year post-transplant. The accrual period will be approximately 3 years with an additional 12 months of follow-up after the accrual period has been completed. Stopping rules are in place for secondary graft failure without autologous recovery and excessive treatment related toxicity. The target sample size for this study is 46 patients with an approximate accrual of 16 patients per year.

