14.0 BIOSTATISTICS

This is a single arm phase 2 trial to investigate the efficacy of a weekly ixazomib regimen to reduce recurrent or late onset acute and chronic GVHD. The primary endpoint of this study is the incidence of recurrent or late acute grade II-IV aGVHD or chronic GVHD from the time of enrollment (day +100 to +150) to 1-year post-transplant time point. In addition to GVHD, the additional treatment failure criteria listed in 12.2 are considered as failures for the primary endpoint. Patients are evaluable for the primary endpoint if they complete at least one cycle of therapy. Patients who discontinue therapy prior to completing one cycle therapy for reasons unrelated to toxicity will be replaced. Patients who prematurely discontinue therapy after completing at least one cycle of therapy will remain evaluable for the primary endpoint.

The historical benchmark for this study is based on patients enrolled on MSK protocol 06-150. With these data, the estimated grade II-IV acute or chronic GVHD at 1-yr post-transplant among patients who could have been eligible to enroll on this study is 63% (no

patient died for reasons unrelated to GVHD). Therefore, the trial is designed such that a one-year incidence of recurrent or late acute grade II-IV GVHD or cGVHD of 40% would be considered promising for further development, whereas a 60% incidence would not be considered worthy of further study. Using these thresholds, we will utilize a Simon's two-stage optimal design based on the proportion of patients who develop GVHD. If more than 10 of the initial 18 patients have recurrent or late acute grade II to IV or cGVHD, the trial will terminate early due to lack of efficacy. Otherwise, the trial will continue to the maximum sample size of 46. If at the end of the study at least 23 out of 46 patients are free of recurrent or late acute grade II-IV GVHD or cGVHD the intervention will be considered promising for further development. The type I and type II errors are both set at 0.10.

In order to reduce patient risk, the study design includes early termination in the event of excessive graft failure or treatment-related mortality during the study period. Stopping rules for excessive failure and corresponding power calculations are given below. The calculations are based on marginal probabilities.

Failure type	Number of failures needed to suspend the study	Failure rate in the population	Probability boundary is crossed

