Secondary graft failure	2 in the first 20	0.02	0.1
	3 at any point	0.15	0.98
Transplant-related 1 yr. mortality	4 in the first 10	0.10	0.07
	5 in the first 20		
	7 in the first 30		
	8 in the first 40	0.30	0.96
	9 at any point		

In addition to the primary objective, there are a number of secondary and safety endpoints included in this study:

Secondary endpoints:

1. Cumulative incidence of cGVHD following study enrollment will be estimated. This will be calculated overall and by severity (moderate/severe). Disease progression and death in the absence of cGVHD are considered competing risks for this analysis.
2. The cumulative incidence of TRM from the time of study enrollment will be estimated, treating disease progression as a competing risk.
3. The cumulative incidence of disease progression from the time of study enrollment will be estimated, treating death in the absence of disease progression as a competing event.
4. The cumulative incidence of grade II-IV and III-IV acute GVHD will be estimated. Disease progression and death in the absence of acute GVHD are considered competing risks for this analysis.
5. Kaplan-Meier methods will estimate overall and progression-free survival from the time of study enrollment.
6. The proportion of patients who are able to discontinue all immunosuppressive medication at one year will be estimated along with a 95% confidence interval.
7. Graphical and summary measures will be used to describe CD3+CD4+ and CD3+CD8+ populations during the study window.

Exploratory Endpoint:

1. The proportion of patients who are able to get vaccines on time will be reported with an exact 95% confidence interval. The vaccine response will be similarly described. Both timing and response will be estimated separately for each vaccine.
2. The treatment failure endpoint will be described separately for patients who enroll on study day +100 to day +125 and for patients who enroll on study day +125 to day +150.

Safety Endpoint:

1. The frequency and severity of adverse events will be tabulated.

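### The crossing probabilities printed for the transplant-related mortality stopping rule (0.07 and 0.96) do not follow from the printed boundary at 46 patients, which gives 0.08 and 0.97

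*Combined protocol and SAP*

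**What the plan says.** Section 14.0 introduces the safety boundaries with "Stopping rules for excessive failure and corresponding power calculations are given below" and adds that the calculations are marginal, so each failure type is assessed on its own.

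The mortality row, "Transplant-related 1 yr. mortality", reads as follows once its cells are put together:

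- "4 in the first 10 0.10 0.07"
- "5 in the first 20"
- "7 in the first 30"
- "8 in the first 40 0.30 0.96"
- a last limit of 9 deaths at any time.

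The decimals are the two assumed true rates (0.10 and 0.30), each followed by the probability that the whole boundary is crossed (0.07 and 0.96).

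The graft-failure row of the same table has limits of 2 in the first 20 patients and 3 at any time, with probabilities 0.1 at a 2% rate and 0.98 at a 15% rate.

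The sample size is the same in both places where it is given: "the trial will continue to the maximum sample size of 46" in section 14.0 and "The target sample size for this study is 46 patients" in section 4.3. No other sample size is given for the table.

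**The concern.** The two probabilities are the only description the plan gives of how the mortality rule performs: how often it would suspend the study when mortality is acceptable, and how often it would do so when mortality is excessive. They should follow from the printed limits and the planned 46 patients, and they do not.

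The size of the gap matters less than what it implies. The limits, the sample size and the probabilities now in the table cannot all come from one calculation, so at least one of them needs checking. If the limits are right, two descriptive figures are slightly wrong. If the probabilities are right, a limit or the sample size behind them differs from what is printed.

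**Working it through.** **Inputs.** Section 14.0: limits 4, 5, 7, 8 and 9; true rates 0.10 and 0.30; maximum of 46 patients; marginal calculation. No outside figure is needed.

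**Method.** Let b(n) be the number of deaths that suspends the study when n patients have been counted: 4 for n up to 10, 5 for 11 to 20, 7 for 21 to 30, 8 for 31 to 40, and 9 for 41 to 46. Let f(n, k) be the probability of having k deaths among n patients without having crossed. Start from f(0, 0) = 1 and apply, for k < b(n),

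f(n, k) = (1 − p) · f(n−1, k) + p · f(n−1, k−1).

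The crossing probability by N patients is 1 − Σ f(N, k), summed over k < b(N). Looking after every patient or only at 10, 20, 30, 40 and 46 gives the same answer, because deaths only accumulate and the limit is constant within each block.

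**Control: the graft-failure row.** With limits 2 (n up to 20) and 3 (after that), N = 46 gives 0.0956 at 2% and 0.9799 at 15%. These round to the printed 0.1 and 0.98, so this row is reproduced.

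**Mortality row.** Cumulative crossing probability with the printed limits:

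| Patients | True rate 0.10 | True rate 0.30 |
|---|---|---|
| 10 | 0.0128 | 0.3504 |
| 20 | 0.0471 | 0.7682 |
| 30 | 0.0560 | 0.8748 |
| 40 | 0.0732 | 0.9547 |
| 46 | 0.0798 | 0.9721 |

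The last six patients add 0.0798 − 0.0732 = 0.0066 and 0.9721 − 0.9547 = 0.0174. A simulation of 400,000 trials at N = 46 gave 0.080 and 0.972. The printed 0.07 and 0.96 are not reproduced.

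**What does give 0.07 and 0.96?**

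| Setting | 0.10 | 0.30 | Rounds to the printed pair? |
|---|---|---|---|
| Printed limits, N = 41 | 0.0732 | 0.9547 | No (0.95) |
| Printed limits, N = 42 | 0.0736 | 0.9568 | Yes |
| Printed limits, N = 43 | 0.0745 | 0.9601 | Yes |
| Printed limits, N = 44 | 0.0758 | 0.9640 | No (0.08) |
| N = 46, last limit 10 | 0.0740 | 0.9617 | Yes |
| N = 46, last limit 11 | 0.0733 | 0.9565 | Yes |
| N = 46, limits read as more than rather than at least | 0.027 | 0.936 | No |
| N = 46, single look at the end, 9 or more | 0.036 | 0.961 | No (0.04) |

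Dropping any one or more of the four interim limits at N = 46 does not give the pair either.

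**Rounding.** Truncating 0.0798 gives 0.07, but truncating 0.9721 gives 0.97, so truncation does not explain both figures.

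**The case against.** The strongest case against raising this is that it changes nothing in the conduct of the trial. The study is suspended by a count of deaths, not by these probabilities. If the counts are as intended, patients have exactly the protection the plan gives them, and detection of excess mortality is slightly better than printed. A false-stop risk of 0.08 rather than 0.07 would not lead anyone to choose a different rule. All of this stands and keeps the point minor. Nor do the documents say that the monitoring committee uses these probabilities, so no such reliance is claimed.

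A reader might also infer that the mortality row was computed for a trial of a different size, or that the two rows describe different trials. The documents do not support that. Sample sizes of 42 or 43 would explain the pair, but so would 46 patients with a last limit of 10 or 11.

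The control is weaker than it looks. The printed 0.1 has one decimal and fits a wide range of sample sizes. Only the 0.98 discriminates, and it fits 45 to 48 patients. It does exclude 42 and 43 for that row (0.968 and 0.972, both rounding to 0.97).

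The plan does not name its computing method. If it was simulation (an assumption), chance might contribute. The nearest values that round to the printed figures are 0.075 and 0.965, which are 0.0048 and 0.0071 away. With 1,000 runs the standard errors are √(0.0798 × 0.9202 / 1000) = 0.0086 and √(0.9721 × 0.0279 / 1000) = 0.0052, so the gaps are about 0.6 and 1.4 standard errors. With 5,000 runs they are about 1.3 and 3. Only a small simulation would make this a comfortable explanation.

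Finally, 46 may not be the exact mortality denominator, because section 14.0 replaces patients who leave before completing one cycle for reasons other than toxicity. If all enrolled patients count (an assumption), the results are 0.086 and 0.979 at 48 patients, and 0.094 and 0.985 at 50. This moves further from the printed pair, so it does not rescue it. It does mean that 0.08 and 0.97 are exact only for 46.

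**Conclusion.** The point holds as a small arithmetic inconsistency. With the printed limits and 46 patients, the crossing probabilities are 0.080 at a 10% rate and 0.972 at a 30% rate, against 0.07 and 0.96 in the table. The false-stop risk is understated by 0.0798 − 0.07 = 0.0098 and the detection probability by 0.9721 − 0.96 = 0.0121, about one percentage point each.

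This rests on independent patients with a common death rate, on limits that act when the count is reached, and on 46 patients counted.

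It would be tempting to conclude that the mortality rule is unsound or that patients are less well protected. The discrepancy alone shows neither. What remains open is whether the probabilities, the last limit or the sample size behind the row is the element in error, and the documents cannot settle that.

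**What to change.** Go back to the source calculation for the mortality row and reconcile its three elements: the limits, the number of patients and the two probabilities. If the printed limits and 46 patients are as intended, restate the row as 0.08 at a 10% rate and 0.97 at a 30% rate. If the source used another sample size or another last limit, say so, correct the element that was misprinted, and compute both rows of the table on the same stated number of patients. The probabilities should not be overwritten before this check, because that could fix in place a last limit that was not intended.

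It would help to add one sentence stating the computing method and whether replaced patients count toward mortality.

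The cost is a look at the original calculation and, in the simplest case, two figures in one table. The printed false-stop risk becomes slightly less favourable and the printed detection probability slightly more so.

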15.1 RESEARCH PARTICIPANT REGISTRATION AND RANDOMIZATION PROCEDURES

15.2 Research Participant Registration

Confirm eligibility as defined in the section entitled Inclusion/Exclusion Criteria. Obtain informed consent, by following procedures defined in section entitled Informed Consent Procedures. During the registration process registering individuals will be required to complete a protocol specific Eligibility Checklist. The individual signing the Eligibility Checklist is confirming whether or not the participant is eligible to enroll in the study. Study staff are responsible for ensuring that all institutional requirements necessary to enroll a participant to the study have been completed. See related Clinical Research Policy and Procedure #401 (Protocol Participant Registration).

15.3 Randomization

This research study does not require randomization procedures.

16.1 DATA MANAGEMENT ISSUES

Research Study Assistant (RSA) will be assigned to the study at MSKCC. The responsibilities of the RSA include project compliance, data collection, abstraction and entry, data reporting, regulatory monitoring, problem resolution and prioritization, and coordination of the activities of the protocol study team.

The data collected for this study will be entered into a secure database Clinical Research Database (CRDB). Source documentation will be available to support the computerized patient record.

16.2 Quality Assurance

Weekly registration reports will be generated to monitor patient accruals and completeness of registration data. Routine data quality reports will be generated to assess missing data and inconsistencies. Accrual rates and extent and accuracy of evaluations and follow-up will be monitored periodically throughout the study period and potential problems will be brought to the attention of the study team for discussion and action.

Random-sample data quality and protocol compliance audits will be conducted by the study team, at a minimum of two times per year, more frequently if indicated.

16.3 Data and Safety Monitoring

The Data and Safety Monitoring Plans (DSM) at Memorial Sloan Kettering Cancer Center were approved by the National Cancer Institute in September 2001. The plans address the new policies set forth by the NCI in the document entitled "Policy of the National Cancer Institute for Data and Safety Monitoring of Clinical Trials" which can be found at: <Http://cancertrials.nci.nih.gov/researchers/dsm/index.html>. The DSM Plans at MSKCC were established and are monitored by the Clinical Research Administration. The MSKCC Data and Safety Monitoring Plans can be found on the MSKCC Intranet at: <https://one.mskcc.org/sites/pub/clinresearch/Documents/MSKCC%20Data%20and%20Safety%20Monitoring%20Plans.pdf>

There are several different mechanisms by which clinical trials are monitored for data, safety and quality. There are institutional processes in place for quality assurance (e.g., protocol monitoring, compliance and data verification audits, therapeutic response, and staff education on clinical research QA) and departmental procedures for quality control, plus there are two institutional committees that are responsible for monitoring the activities of our clinical trials programs. The committees: *Data and Safety Monitoring Committee (DSMC)* for Phase I and II clinical trials, and the *Data and Safety Monitoring Board (DSMB)* for Phase III clinical trials, report to the Center's Research Council and Institutional Review Board.

During the protocol development and review process, each protocol will be assessed for its level of risk and degree of monitoring required. Every type of protocol (e.g., NIH sponsored, in-house sponsored, industrial sponsored, NCI cooperative group, etc.) will be addressed, and the monitoring procedures will be established at the time of protocol activation.

17.1 PROTECTION OF HUMAN SUBJECTS

17.2 Privacy

MSK's Privacy Office may allow the use and disclosure of protected health information pursuant to a completed and signed Research Authorization form. The use and disclosure of protected health information will be limited to the individuals described in the Research Authorization form. A Research Authorization form must be completed by the Principal Investigator and approved by the IRB and Privacy Board (IRB/PB).

17.3 Serious Adverse Event (SAE) Reporting

An adverse event is considered serious if it results in ANY of the following outcomes:

- Death
- A life-threatening adverse event
- An adverse event that results in inpatient hospitalization or prolongation of existing hospitalization
- A persistent or significant incapacity or substantial disruption of the ability to conduct normal life functions
- A congenital anomaly/birth defect

- Important Medical Events (IME) that may not result in death, be life threatening, or require hospitalization may be considered serious when, based upon medical judgment, they may jeopardize the patient or subject and may require medical or surgical intervention to prevent one of the outcomes listed in this definition

Note: Hospital admission for a planned procedure/disease treatment is not considered an SAE.

SAE reporting is required as soon as the participant signs consent and is registered. SAE reporting is required for 30-days after the participant's last investigational treatment or intervention. Any events that occur after the 30-day period and that are at least possibly related to protocol treatment must be reported.

An SAE must be reported to the IRB/PB within 5 calendar days of the event. The IRB/PB requires a Clinical Research Database (CRDB) SAE report be submitted electronically to the SAE Office as follows:.

For IND/IDE trials: Reports that include a Grade 5 SAE should be sent to [contact]. All other reports should be sent to [contact].

For all other trials: Reports that include a Grade 5 SAE should be sent to [contact]. All other reports should be sent to [contact].

The report should contain the following information:

Fields populated from CRDB:

- Subject's name (generate the report with only initials if it will be sent outside of MSK)
- Medical record number
- Disease/histology (if applicable)
- Protocol number and title

Data needing to be entered:

- The date the adverse event occurred
- The adverse event
- The grade of the event
- Relationship of the adverse event to the treatment (drug, device, or intervention)
- If the AE was expected
- The severity of the AE
- The intervention
- Detailed text that includes the following
 - A explanation of how the AE was handled
 - A description of the subject's condition
 - Indication if the subject remains on the study
 - If an amendment will need to be made to the protocol and/or consent form.

The PI's signature and the date it was signed are required on the completed report.

For IND/IDE protocols:

The CRDB AE report should be completed as above. If appropriate, the report will be forwarded to the FDA by the SAE staff through the IND Office. Potentially serious toxicities are an expected part of transplant therapy. Adverse events (AEs) and serious adverse events (SAEs) will be captured and reported as outlined in the Departmental Standard Working Procedure titled "Adult Bone Marrow Transplant (BMT) Adverse Event (AE) and Serious Adverse Event (SAE) Guide". In addition, the expected adverse events outlined in Table 11.2 will be captured.

17.2.1

AEs which are serious must be reported to Takeda Pharmaceuticals/ Millennium Pharmacovigilance (or designee) from the first dose of study drug through 30 days after administration of the last dose of ixazomib. Any SAE that occurs at any time after completion of ixazomib treatment or after the designated follow-up period that the sponsor-investigator and/or sub-investigator considers to be related to any study drug must be reported to Takeda Pharmaceuticals/ Millennium Pharmacovigilance (or designee). In addition, new primary malignancies that occur during the follow-up periods must be reported, regardless of causality to study regimen, for a minimum of three years after the last dose of the investigational product, starting from the first dose of study drug. All new cases of primary malignancy must be reported to Takeda Pharmaceuticals/ Millennium Pharmacovigilance (or designee).

17.3.2 Serious Adverse Event Definition

Serious AE (SAE) means any untoward medical occurrence that at any dose:

- Results in **death**.
- Is **life-threatening** (refers to an AE in which the patient was at risk of death at the time of the event. It does not refer to an event which hypothetically might have caused death if it were more severe).
- Requires inpatient **hospitalization or prolongation of an existing hospitalization** (see clarification in the paragraph below on planned hospitalizations).
- Results in **persistent or significant disability or incapacity**. (Disability is defined as a substantial disruption of a person's ability to conduct normal life functions).
- Is a **congenital anomaly/birth defect**.
- Is a **medically important event**. This refers to an AE that may not result in death, be immediately life threatening, or require hospitalization, but may be considered serious when, based on appropriate medical judgment, may jeopardize the patient, require medical or surgical intervention to prevent 1 of the outcomes listed above, or involves

suspected transmission via a medicinal product of an infectious agent. Examples of such medical events include allergic bronchospasm requiring intensive treatment in an emergency room or at home, blood dyscrasias or convulsions that do not result in inpatient hospitalization, or the development of drug dependency or drug abuse; any organism, virus, or infectious particle (e.g., prion protein transmitting transmissible spongiform encephalopathy), pathogenic or nonpathogenic, is considered an infectious agent.

Clarification should be made between a serious AE (SAE) and an AE that is considered severe in intensity (Grade 3 or 4), because the terms serious and severe are NOT synonymous. The general term *severe* is often used to describe the intensity (severity) of a specific event; the event itself, however, may be of relatively minor medical significance (such as a Grade 3 headache). This is NOT the same as *serious*, which is based on patient/event outcome or action criteria described above, and is usually associated with events that pose a threat to a patient's life or ability to function. A severe AE (Grade 3 or 4) does not necessarily need to be considered serious. For example, a white blood cell count of 1000/mm³ to less than 2000 is considered Grade 3 (severe) but may not be considered serious. Seriousness (not intensity) serves as a guide for defining regulatory reporting obligations.

